6.6.2. Adverse Events

AEs will be graded by investigators using CTCAE version 5.0. The AE verbatim descriptions (investigator terms from the eCRF) will be classified into standardized medical terminology using MedDRA. Adverse events will be coded to the MedDRA (Version 25.1 or higher) lowest level term closest to the verbatim term, along with the linked MedDRA preferred term (PT) and primary system organ class (SOC).

A treatment-emergent adverse event (TEAE) is defined as an AE that had onset or increase in severity level date on or after the date of the first dose of study drug through 40 days after the last dose (permanent discontinuation of study drug) or the initiation of new anti-cancer therapy, whichever is earlier. Summary tables will generally focus on those AEs that were treatment-emergent (TE). All AEs, treatment-emergent or otherwise, will be presented in patient data listings.

An AE overview table, including the number and percentage of patients with TEAEs, treatment-emergent serious adverse events (SAEs), TEAEs with Grade 3 or above, TEAEs that led to death, TEAEs that led to treatment discontinuation, TEAEs that led to dose reduction, TEAEs that led to dose interruption, TEAEs that led to dose delay, treatment-related TEAEs grade 3 or

above. Treatment-related AEs include those events considered by the investigator to be related to study drug or with a missing assessment of the causal relationship.

The incidence of TEAEs will be reported as the number (percentage) of patients with TEAEs by SOC, PT and the worst grade. A patient will be counted only once by the highest severity grade within an SOC and PT, even if the patient experienced more than 1 TEAE within a specific SOC and PT. The number (percentage) of patients with treatment-emergent SAEs, treatment-related TEAEs, TEAEs with grade 3 or above, treatment-related SAEs, TEAEs that led to death, and TEAEs that led to treatment discontinuation, dose modifications, and infusion-related reactions will be summarized by SOC and PT. TEAEs with grade 3 or above will also be summarized by PT in descending order.

Patient data listings of SAEs, fatal AEs will be provided.

All deaths and causes of death will be summarized including those occurred during the study treatment period and those reported during the safety follow-up period after treatment completion/discontinuation.

6.6.3. Laboratory Values

Laboratory safety tests will be evaluated for selected parameters described in [Table 2](#).

Descriptive summary statistics (n, mean, standard deviation, median, minimum, maximum for continuous variables; n [%] for categorical variables) for laboratory parameters and their changes from baseline will be summarized by visit.

Laboratory parameters ALT, AST, total bilirubin, hemoglobin, platelet counts, WBC count, neutrophil and lymphocyte that are graded in NCI CTCAE Version 5.0 will be summarized by shifts from baseline CTCAE grades to maximum post-baseline grades. In the summary of laboratory parameters by CTCAE grade, parameters with CTCAE grading in both high and low directions will be summarized separately.

Patient data listings of all laboratory data collected will be provided.

Table 2: Laboratory Tests

Clinical chemistry	Hematology	Coagulation	Urinalysis
Alanine aminotransferase	Hemoglobin	Prothrombin time	Glucose
Aspartate aminotransferase	Platelet count	Activated partial thromboplastin time	Protein
Total bilirubin	White blood cell count	International normalized ratio	Blood
Potassium	Lymphocyte count		Ketones
Sodium	Neutrophil count		
Total calcium	Basophils		
Creatinine			

Clinical chemistry	Hematology	Coagulation	Urinalysis
Chloride C-reactive protein Gamma-glutamyl transferase			

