7.6. Discontinuation From Study Treatment or From the Study

7.6.1. Patient Discontinuation From Study Treatment (End of Treatment for an Individual Patient)

Patients have the right to discontinue study drug at any time for any reason. In addition, the investigator has the right to discontinue a patient from study drug at any time. Patients who discontinue study drug for reasons other than relapse or progressive disease (PD) should be followed for assessments of preliminary anticancer activity (Section 8.4) and safety (Section 8.2), if possible.

The primary reason for discontinuation from study drug should be documented on the appropriate eCRF. Patients may discontinue study drug for reasons including but not limited to the following:

- Relapse
- PD
- AE
- Patient decision
- Pregnancy
- Any medical condition that the investigator or sponsor determines may jeopardize the patient's safety if he or she were to continue the study drug
- Use of any concurrent anticancer therapy, including chemotherapy, hormonal therapy, immunotherapy, standard or investigational agents (including Chinese [or other Country] herbal medicine and Chinese [or other Country] patent medicines) for the treatment of cancer [regardless of cancer type])
- Patient noncompliance
 - Study site staff should first counsel patients who are significantly noncompliant (eg, missing 2 treatment cycles) on the importance of study drug compliance and drug accountability. The investigator may, in consultation with the medical monitor, discontinue patients from treatment who are consistently noncompliant.

Treatment with dinutuximab beta should be permanently discontinued if the following toxicities occur:

• Grade 3 or 4 anaphylaxis

- Prolonged Grade 2 peripheral motor neuropathy
- Grade 3 peripheral neuropathy
- Grade 3 vision eye toxicity
- Grade 4 hyponatremia (< 120 mEq/L) despite appropriate fluid management
- Recurrent or Grade 4 capillary leak syndrome (requires ventilator support)

If dinutuximab beta or 13-cis-RA is discontinued permanently before cycle 5 for reasons other than relapse or PD, the other drug could be continued per the study protocol.

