Occasional occurrences of peripheral neuropathy have been reported with dinutuximab beta. Cases of motor or sensory neuropathy lasting > 4 days must be evaluated and non-inflammatory causes such as disease progression, infections, metabolic syndromes, and concomitant medication should be excluded.

Treatment should be permanently discontinued in patients experiencing any objective prolonged weakness attributable to dinutuximab beta administration. For patients with moderate (Grade 2) neuropathy (motor with or without sensory), treatment should be interrupted and may be resumed after neurologic symptoms resolve.

Systemic Infections

Patients are likely to be immunocompromised as a result of prior therapies. As they typically have a central venous catheter in situ, they are at risk of developing systemic infection. Patients should have no evidence of systemic infection and any identified infection should be controlled before starting therapy.

Hematologic Toxicities

Occurrence of hematologic toxicities such as erythropenia, thrombocytopenia, or neutropenia has been reported with dinutuximab beta. Grade 4 hematologic toxicities improving to \leq Grade 2 or baseline values by start of next treatment course do not require dose modification.

Laboratory Abnormalities

Regulatory monitoring of liver function and electrolytes is recommended.

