10.2.3. Laboratory Analyses

Clinical laboratory (eg, hematology, clinical chemistry) values will be evaluated for each laboratory parameter as appropriate. Abnormal laboratory values will be flagged and identified as those outside (above or below) the normal range. Reference (normal) ranges for laboratory parameters will be provided. Descriptive summary statistics (eg, n, mean, standard deviation, median, minimum, and maximum for continuous variables; n [%] for categorical variables) for laboratory parameters and their changes from baseline will be calculated. Laboratory values will be summarized by visit and by visit with the maximum postbaseline change.

Laboratory parameters that are graded by NCI-CTCAE version 5.0 or higher will be summarized by NCI-CTCAE grade. In the summary of laboratory parameters by NCI-CTCAE grade, parameters with NCI-CTCAE grading in both high and low directions (eg, calcium, glucose, magnesium, potassium, and sodium) will be summarized separately.

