APPENDIX 2. CLINICAL LABORATORY ASSESSMENTS

Table 8: Protocol-Required Safety Laboratory Assessments

Clinical chemistry	Hematology	Coagulation	Urinalysis ^a
Alanine aminotransferase Aspartate aminotransferase Total bilirubin Potassium Sodium Total calcium Creatinine Chloride C-reactive protein Gamma-glutamyl transferase	Hemoglobin Platelet count White blood cell count Lymphocyte count Neutrophil count Basophils	Prothrombin time Activated partial thromboplastin time International normalized ratio	Glucose Protein Blood Ketones

In case of abnormal result: urinary sediment assessment (red blood cells per high-power field, white blood cells per high-power field, cellular casts)

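### The SAP's only CTCAE-graded laboratory table omits sodium, potassium and calcium, which the protocol names for grading, and the SAP does not declare the change (minor)

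*SAP*

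**What the plan says.** Protocol 10.2.3 sets a general rule without a restricted list: "Laboratory parameters that are graded by NCI-CTCAE version 5.0 or higher will be summarized by NCI-CTCAE grade". It then gives examples of analytes graded in two directions: "parameters with NCI-CTCAE grading in both high and low directions (eg, calcium, glucose, magnesium, potassium, and sodium) will be summarized separately".

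SAP 6.6.3 names eight analytes, "Laboratory parameters ALT, AST, total bilirubin, hemoglobin, platelet counts, WBC count, neutrophil and lymphocyte that are graded in NCI CTCAE Version 5.0", and says that these "will be summarized by shifts from baseline CTCAE grades to maximum post-baseline grades". It keeps a sentence on summarising the two directions separately, but without the protocol's examples. No other graded laboratory output is specified. For all laboratory parameters, SAP 6.6.3 also plans by-visit descriptive statistics (including minimum and maximum, for values and for changes from baseline) and full patient listings.

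The chemistry panel in Protocol Appendix 2 includes "Total bilirubin Potassium Sodium Total calcium Creatinine Chloride C-reactive protein Gamma-glutamyl transferase", and SAP Table 2 repeats it.

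Two other protocol passages concern electrolytes. Section 9.6 states: "Regulatory monitoring of liver function and electrolytes is recommended". Section 7.6.1 lists, among the toxicities for permanent discontinuation of dinutuximab beta, "Grade 4 hyponatremia (< 120 mEq/L) despite appropriate fluid management".

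SAP Section 8 records one departure from the protocol, the removal of the summary of important protocol deviations.

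**The concern.** The protocol promises a graded summary for electrolytes and the SAP, followed as written, does not deliver it. Because SAP Section 8 does declare another change, a reader would assume that laboratory grading still follows the protocol.

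Safety is a primary endpoint, and liver tests and electrolytes are the two laboratory groups that Protocol 9.6 singles out for monitoring. The SAP grades the main liver tests and no electrolyte. At stake is a simple safety count: how many patients reached each worst grade of low or high sodium, potassium or calcium, set against their baseline grade.

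**Working it through.** The documents state no figure to reproduce. The check compares lists and then asks what the remaining outputs can show.

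**1. Analytes in the SAP shift summary (SAP 6.6.3).** ALT, AST, total bilirubin, hemoglobin, platelets, WBC, neutrophils, lymphocytes: 8.

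**2. Collected blood tests (Protocol Appendix 2; SAP Table 2).** Chemistry 10 + hematology 6 + coagulation 3 = 19. Not in the shift summary: 19 − 8 = 11, namely potassium, sodium, total calcium, creatinine, chloride, C-reactive protein, GGT, basophils, PT, aPTT and INR. This count is not the size of the gap, because the documents do not say which of the 11 are graded by CTCAE.

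**3. The protocol's own examples (Protocol 10.2.3).**

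| Named example | In the collected chemistry panel | In the SAP shift list |
|---|---|---|
| Calcium | yes | no |
| Potassium | yes | no |
| Sodium | yes | no |
| Glucose | no (urinalysis only) | no |
| Magnesium | no | no |

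Of 5 named examples, 3 are collected in blood and 0 are in the SAP list. Those three are the firm contradiction. Glucose and magnesium cannot be graded from the planned chemistry panel at all.

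**4. What the other outputs give for an electrolyte.**

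- *By-visit tables.* In Protocol Appendix 1, biochemistry falls on Days 1, 8, 11, 15, 22 and 29 of each cycle, and at screening, end of treatment and safety follow-up. For a patient completing five cycles that is 6 × 5 + 3 = 33 scheduled values. Leaving out screening and Cycle 1 Day 1, both before the first dose, 33 − 2 = 31 are post-baseline. Minimum and maximum are printed at each visit, but nothing combines the visits into one worst grade per patient. The SAP does not say whether repeat or unscheduled tests enter these tables. Protocol 10.2.3 also mentions a summary at the maximum post-baseline change, which SAP 6.6.3 does not carry over.
- *Listings.* With 8 patients completing all cycles there are up to 8 × 31 = 248 scheduled post-baseline values per analyte. Everything is there, but the reader must find and grade each patient's worst value by hand.
- *Adverse-event tables.* Under Protocol 9.2.5 a laboratory abnormality becomes an adverse event when the investigator judges it clinically significant. SAP 6.6.2 then reports it by worst grade.

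**5. What is missing.** No planned output counts patients by worst electrolyte grade, against baseline grade, using every measured value irrespective of that judgement.

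**The case against.** The strongest reply is that nothing important can be missed.

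- *The stopping event is covered.* A reader might infer that hyponatremia severe enough to stop treatment has no planned summary by grade. The documents do not support that. Protocol 9.2.5 counts abnormalities that lead to interruption or discontinuation among those generally regarded as clinically significant, and uses hyperkalemia as an example of how to record one. SAP 6.6.2 would then show the event by worst grade, among events of Grade 3 or above, and among events leading to discontinuation. The criterion also carries the qualifier about fluid management, which a laboratory shift table cannot show.
- *Extremes are not buried in averages.* A reader might infer that by-visit summaries would dilute one patient's extreme value. The same tables print minimum and maximum for values and for changes, and all data are listed for about 8 patients.
- *The protocol's wording is partly generic.* Its examples include two analytes that the chemistry panel does not collect, and it asks for a summary by grade, not a shift table. Section 9.6 concerns monitoring, which is retained.
- *Creatinine is not named.* Protocol 10.2.3 does not mention it, and the documents do not say that it is graded. It can be claimed only under the general rule.

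All of this stands and keeps the point small. It does not remove it. The general rule in Protocol 10.2.3 is explicit and three collected analytes are named under it. The shift summary is the SAP's only graded laboratory output, so there is no other place where the promise could be met. Adverse-event tables depend on a judgement that a graded laboratory summary does not need.

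It would also go too far to call the SAP's two-directional sentence empty, since the documents do not establish that none of the eight listed analytes is graded in both directions.

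**Conclusion.** The mismatch is real and undeclared, and it is minor. For sodium, potassium and total calcium the SAP omits a graded summary that the protocol promises. The loss is an objective per-patient worst-grade count for those three analytes. Collection, by-visit summaries, listings and adverse-event reporting are unaffected, and no safety signal need be lost.

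This rests on reading the eight names in SAP 6.6.3 as a closed list, which is the plain sense of the sentence, and on SAP Section 8 being the complete record of departures from the protocol. For analytes other than the three electrolytes, including creatinine, the point holds only if CTCAE version 5.0 grades them. The point takes no position on the discontinuation criterion itself.

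**What to change.** In SAP 6.6.3, add sodium, potassium and total calcium to the shift summary from baseline to worst CTCAE grade, with high and low directions separate. Add any other collected analyte that CTCAE version 5.0 grades, creatinine included if that applies. With the three electrolytes the list grows from 8 to 8 + 3 = 11 analytes, or 12 with creatinine; the electrolytes contribute 3 × 2 = 6 directional shifts. If the sponsor prefers the shorter list, SAP Section 8 should record the restriction and give a reason.

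The cost is a few rows in a table already planned, with no new data and no change to study conduct.

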6.6.4. Vital Signs

Descriptive statistics for vital sign parameters systolic and diastolic blood pressure (BP), pulse rate, temperature, and weight and changes from baseline will be presented by visit.

6.6.5. Electrocardiograms (ECG)

Actual value and change from baseline for the QT interval, heart rate and corrected QT interval by Fredericia (QTcF) will be summarized. The average of the readings for the visit will be used for the summary.

The number and percentage of patients satisfying the following QT and QTcF conditions at any time post-baseline will be summarized:

- 450, > 480, or > 500 msec
- maximum increase > 30 or > 60 msec

6.7. Pharmacokinetic Analyses

Actual dose and blood draw times will be used to calculate the PK parameters. Parameters will be listed individually and summarized using descriptive statistics.

The following PK parameters will be calculated as appropriate for the data collected. Other PK parameters may be calculated if supported by the data.

- C_{max} : Maximum serum concentration
- t_{max} : Time to maximum serum concentration
- C_{min} : Minimum serum concentration
- $t_{1/2}$: Half-life
- AUC_{0-t} : Area under the serum concentration-time curve from zero to the last measurable concentration
- $AUC_{0-\infty}$: Area under the serum concentration-time curve from zero to infinity

Calculation and presentation of PK parameters will be based on the Work Instruction: Best Practice Guidance: Non-Compartmental Pharmacokinetic Data Analysis for Clinical Studies. Version 1.0, Document Number VV-QDOC-13140.

6.7.1. Reporting of Pharmacokinetic Concentrations for Descriptive Statistics

The PK analyst will appropriately flag and annotate treatment of any anomalous concentrations, exclusions and any special treatment for descriptive statistics and plots. The concentration and time data will be listed individually and summarized using descriptive statistics.

The following conventions will be used for reporting descriptive statistics for concentration data.

- PK concentrations should be reported in listings at the same level of precision as that in the source data.
- If a concentration at a given time point is below the assay quantification limit (BLQ), the concentration shall be reported as the term “BLQ” with the lower limit of quantitation (LLOQ) defined in the footnotes. BLQ values shall be treated as zero for computation of descriptive statistics. BLQ values will not be included for calculations of geometric mean and geometric coefficient of variation (CV%).
- If the calculated mean concentration is BLQ, the mean value shall be reported in outputs (such as tables) as BLQ and SD and geometric CV% shall be reported as ND (not determined). Minimum, median, and maximum may be reported.

6.7.2. Plots of Pharmacokinetic concentrations

Concentration versus time data will be plotted individually and summarized graphically using arithmetic mean (+SD) plots by treatment group, respectively in linear and log-linear scale. Arithmetic mean concentrations that are BLQ shall be set to zero for plotting on both linear scale but not shown in log-linear scale.

6.7.3. Reporting of PK parameters for Descriptive Statistics

The PK analyst will appropriately flag and annotate treatment of any anomalous PK parameters, exclusions and any special treatment for descriptive statistics.

- All the PK parameters should have at least the following summary statistics: sample size (n), mean, standard deviation (SD), coefficient of variance (CV%), median, minimum, maximum, geometric mean, geometric CV%.
- For in-text tables, Geometric mean (geometric CV%) will be the default method of reporting PK parameters. t_{max} should be presented as median, range (minimum, maximum), when presenting the summary statistics. $t_{1/2}$ should be presented as geometric mean, range (minimum, maximum).
- For any parameters that $n \leq 2$, SD should not be presented.
- The units for all PK parameters will be provided.

- It is recognized that the number of decimals in reported concentrations, for example: “9632.94401 ng/mL” or “9.963294401 ug/mL” are highly improbable and will be queried (since bioanalytical assays generally do not have this level of precision). Usually the first-in-human dose escalation trial will provide the numerical range of PK parameters eg. AUC range from 10 to 10,000 ng.hr/mL and C_{max} range from 1 to 1000 ng/mL.

In this scenario, for reporting PK parameters such as AUC and C_{max}, the following guidance is provided for rounding:

- If the numerical value is below 100 then one decimal place may be used eg, 0.1 or 99.9.
- For values ranging from >100, whole numbers should be used eg, 100 or 9999.
- If > 10,000 the clinical pharmacologist may decide on changing units eg, from µg/ml to mg/ml.
- For reporting times eg, for t_{max} or t_{1/2}, if <1 hr use 2 decimals; time up to 24 hr should be reported to one decimal place eg., 23.5 hr, time >24 hr should be rounded to nearest whole number eg, 105 hr.

7. INTERIM ANALYSES

No interim analysis is planned.

8. CHANGES IN THE PLANNED ANALYSIS

Table 3: Statistical Analysis Plan Changes

SAP version	Approval date	Change made from	Rationale of the change	Description of the change
1.0	06 July, 2023	Protocol Amendment 1.0	No or very few important protocol deviations are expected.	Remove summary of important deviations.

APPENDIX 1. SCHEDULE OF ASSESSMENT

	Screening (Day -28 to Day -1)	Cycles 1 to 5																EOT/early termination ^b	Safety follow-up ^c		
		Day 1 ^a	Day 2	Day 3	Day 4	Day 5	Day 6	Day 7	Day 8	Day 9	Day 10	Day 11 ^a	Day 12	Day 15	Day 22	Day 25	Day 29			Day 35	
Visit day																				-7 to 7 days or 0 to 7 days	+ 40 days
Visit window		± 3																			± 7
Informed consent	X																				
Inclusion/exclusion criteria	X																				
Demography	X																				
Medical history	X																				
Oxygen saturation on room air	X	X																			X
Pregnancy test in WOCBP ^d	X	X																			
HBsAg/HCV-Ab ^e	X																				
Ophthalmologic examination	X																			X	X
Height/weight	X	X																			
Physical examinations ^f	X	X-----X																		X	X
Vital signs	X	X-----X																		X	X
Performance status	X	X-----X																		X	X
ECHO or MUGA scan	X	As clinically indicated																X	X		
12-Lead ECG ^g	X	X										X								X	X
Chest X-Ray ^h		X	As clinically indicated																		
Complete blood count (including differential count)/biochemistry ^{i,j}	X	X									X			X	X		X			X	X
Urinalysis ^{i,j}	X	X																		X	X
Coagulation ^{i,j}	X	X																		X	X

Dinutuximab beta infusion ^k		X-----Continuous infusion-----X																
13-cis-RA												X-----X						
PK sampling in Cycle 1 ^l		X		X					X			X	X ^m	X ^m		X		
PK sampling in Cycle 2-4 ^l		X									X							
Tumor assessments ⁿ	X																X	
Adverse events	X-----X																	
Concomitant medications ^o	X-----X																	

Abbreviations: AE, adverse event; CT, computed tomography; ECG, electrocardiogram; ECHO, echocardiography; EOT, end of treatment; HBsAg, hepatitis B surface antigen; HCV-Ab, hepatitis C virus antibody; INRC, international neuroblastoma response criteria; MIBG, metaiodobenzylguanidine; MRI, magnetic resonance imaging; MUGA, multigated acquisition scan; PK, pharmacokinetic(s); QTcF, QT interval corrected for heart rate using Fridericia’s formula; WOCBP, woman of childbearing potential; ¹²³I, iodine-123.

- ^a Day 1 evaluations must be done before the start of the dinutuximab beta infusion. Day 11 evaluations must be done just before the end of the dinutuximab beta infusion.
- ^b The EOT Visit is conducted within ± 1 week of the end of Cycle 5. For early termination, the EOT Visit is conducted ≤ 7 days after the investigator determines that the patient must permanently discontinue the study drug or the patient decides to withdraw from the study before the end of Cycle 5.
- ^c Safety Follow-up Visit: within 40 days [± 7 days] after last dose of study drug; initiation of new anticancer therapy, death, withdrawal of consent, or loss to follow-up, whichever comes first.
- ^d Pregnancy test in WOCBP is described in Appendix 4 of the protocol.
- ^e If HCV-Ab positive, HCV-RNA test will be required for eligibility check.
- ^f Physical examinations is presented in Section 8.2.2 of the protocol.
- ^g At each timepoint, 3 consecutive 12-lead ECGs should be performed approximately 2 minutes apart to determine the mean QTcF interval.
- ^h Chest X-ray should be performed within 7 days before the start of dinutuximab beta infusion in each cycle. It can be skipped if chest MRI or CT scan has been performed already before administration per investigator’s discretion.
- ⁱ If clinical chemistry, hematology, coagulation and urinalysis at screening are not performed ≤ 7 days before study drug administration on Day 1 of Cycle 1, these tests should be repeated and reviewed before study drug administration. After Day 1 of Cycle 1, results are to be reviewed within 72 hours before study drug administration (Section 8.2.5 of the protocol).
- ^j The test for clinical chemistry, hematology, coagulation, and urinalysis, excluding PK sampling, will be performed within 72 hours before study drug administration on Day 1 of each cycle. All laboratory tests with values considered clinically abnormal during participation in the study or within 40 days after the last dose of study drug should be repeated until the values return to normal or baseline or are no longer considered clinically significant by the investigator or medical monitor (Section 8.2.5 of the protocol).
- ^k The recommended dose of dinutuximab beta depends on the patient’s body surface area (BSA) and the actual dose is calculated on every Day 1 of Cycle 1 to 5 (BSA = SQRT [weight (kg) x height (cm)/ 3600]).
- ^l PK sampling time refers to [Table 4](#).
- ^m PK sampling on Day 15 and Day 22 in Cycle 1 is optional.
- ⁿ Tumor assessments will be performed by the investigators at Screening Visit, end of treatment Cycle 3 and end of treatment Visit per their clinical practice. The INRC ([Brodeur et al 1993](#)) is recommended as a reference for response evaluation in patients evaluable for response. Tumor assessments may include MRI and/or CT scan and/or ¹²³I-MIBG scan and/or ¹⁸F-FDG-PET and/or bone marrow assessment.
- ^o Concomitant medications will be defined as medications that started before the first dose of study drug(s) and were continuing at the time of the first dose of study drug(s), or started on or after the date of the first dose of study drug(s) up to 40 days after the patient’s last dose (as of the Safety Follow-up Visit) in Section 10.1.5 of the protocol.

X: evaluations must be regularly repeated during the timepoints indicated according to routine medical care to ensure safe treatment of the patient.

Table 4: Dinutuximab Beta PK Sampling Schedule

Cycle	Cycle 1 (35 days per cycle)							Cycle 2, 3, and 4	
Time	D1 Predose	D3	D8	D11	D15 ^a	D22 ^a	D29	D1 Predose	D11
Window Allowed	-30 mins ^b	± 1 h ^c	± 1 h ^c	-5 mins ^d				-30 mins ^b	-5 mins ^d
PK Serum Sample	X	X	X	X	X	X	X	X	X

Abbreviation: PK, pharmacokinetic(s).

^a PK sampling on Day 15 and Day 22 in Cycle 1 is optional. That adjustment needs to be aligned with pharmacologists. PK sampling on Day 29 in Cycle 1 is required even if the infusion time will be delayed or extended.

^b 30 minutes before starting infusion.

^c Infusion starting time ± 1 hour.

^d 5 minutes before the end of infusion, even if the infusion time will extend to the next days.

